#### 4.1.4 4-week Baseline Symptom Assessment (Placebo Run-in)

To enter this phase, subjects must:

• Meet all inclusion criteria that are possible to assess prior to the 4-week Baseline Symptom Assessment including the Global EoE score >3 (Inclusion Criterion #5; EoE score must remain >3 at each of Visits 1, 2 and 3 before randomization, or the subject will be considered a screen failure) except those to be assessed during the 4-week Baseline Symptom Assessment: Inclusion Criterion #7: evidence of EoE as defined by ≥15 PEAK eosinophils/HPF; Inclusion Criterion #8: in the daily diary, report episodes of dysphagia ≥3 days per 7 days during the last 14 days of the 4-week Baseline Symptom Assessment; Inclusion Criterion #9: completion of the daily diary on at least 5 out of each 7 days during the last 14 days of the Baseline Symptom Assessment;

Meet no exclusion criteria that will be assessed prior to the 4-week Baseline Symptom
Assessment (i.e., all except Exclusion Criteria #24: a serum cortisol level <16 μg/dL
(440 nmol/L) at 60 minutes with adrenocorticotropic hormone [ACTH] stimulation test
using 250 μg cosyntropin administered intramuscularly [i.e., an abnormal result on the
ACTH stimulation test]). The ACTH stimulation test should have been completed before
entry into the 4-week Baseline Symptom Assessment, however the results of the test may
be pending.

The subject will complete a site visit at the beginning of the 4-week Baseline Symptom Assessment to complete procedures and assessments noted in Table 4-1.

During the 4-week Baseline Symptom Assessment, baseline symptom severity will be determined and the ability of the subject to be compliant with diary entries will be assessed. Pathology for EGD biopsies may also be assessed (or earlier if possible).

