#### **Before Entering 4-week Baseline Symptom Assessment**

- 1. Male or female between  $\ge 18$  and  $\le 75$  years of age at the time of informed consent;
- 2. Signed the ICF and willing and able to adhere to all study procedures;
- 3. Diagnosis or presumptive diagnosis of EoE;
  - Diagnosis of EoE must be confirmed by symptoms, histology, and historical documentation of failed treatment on ≥8 weeks of high-dose PPI, as determined by the Investigator. High-dose PPI is defined as 20 to 40 mg BID of any marketed PPI or alternatively this total dose administered once daily; maintenance doses of PPIs are not acceptable.

Note: Documentation of PPI failure prior to initial diagnosis or by documentation of PPI failure at the time of Screening is required. The subjects may be pre-screened but should not be consented, sign an ICF, or be offered participation in FLUTE if they have not met the diagnostic criteria for EoE that requires that they fail an 8-week trial of high-dose PPIs except those who have taken PPIs for 8 weeks will use the EGD within the study for this documentation. The Investigator and potential subject must make the decision to complete a PPI trial independent of any considerations of the study. There is insufficient time to do the 8-week trial within the current study. Should a subject be consented in error and screen fails due to this point, they may be re-screened (see Section 4.1.3).

- 4. Have a subject-reported history of ≥3 episodes of dysphagia (difficulty with food going down or an awareness of the sensation of food going down the esophagus) in the 7 days prior to Screening;
- 5. Have a 7-day Global EoE Symptom Score >3 at baseline (EoE score must remain >3 at each of Visits 1, 2 and 3 before randomization). This will be performed on paper during the Screening Visit.
- 6. Willing and able to adhere to study-related treatment regimens, procedures, and visit schedule.

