#### 8.8.3 Secondary and Exploratory Efficacy Analysis

Statistical tests to compare each APT-1011 dosing group with placebo will be performed for the secondary efficacy endpoints, but the corresponding p-values will be considered as descriptive rather than inferential. The secondary endpoints will be analyzed via a Cochran-Mantel-Haenzel test for categorical endpoints and analysis of covariance for change from baseline endpoints, except for the endpoint of time to relapse after initiation of double-blind treatment in Part 2, which will be analyzed using Kaplan-Meier methods.

As a secondary efficacy analysis, all 4 doses of active treatment will be pooled and compared to placebo with a one-sided test of two proportions.

Additionally,

a logistic regression model using both dose and frequency and dose-frequency interaction will be used to analyze the primary endpoint. Formal statistical hypothesis testing will be used to

Adare Pharmaceuticals SP-1011-002 APT-1011

evaluate treatment benefit with respect to the reduction in number of dysphagia episodes. For each dose that meets the criterion for statistical significance on the primary efficacy outcome, a Wilcoxon Rank-Sum test will be used to test whether the reduction in the number of dysphagia episodes from baseline is larger for the treatment group compared to the control. The hypothesis to be tested is:

 $H_0: R_{1i}(x) \leq R_{0i}(x)$ 

 $H_1: R_{1j}(x) > R_{0j}(x)$ 

Where  $R_{ij}(x)$  is the distribution function for the reduction in number of dysphagia episodes for treatment group i (=0 for control, 1 for treatment) and dose j. Holm's step-down procedure will be used to control the overall Type I error at 0.05, where the number of doses considered for inferential testing is equal to the number of doses that meet statistical significance for the primary efficacy analysis.

Statistical tests to compare each APT-1011 dosing group with placebo will be performed for other secondary efficacy endpoints, but the corresponding p-values will be considered as descriptive rather than inferential. The secondary endpoints will be analyzed via a stratified Cochran-Mantel-Haenzel test for categorical endpoints and analysis of covariance or Wilcoxon Rank-Sum tests for change from baseline endpoints, except for the endpoint of time to relapse after initiation of double-blind treatment in Part 2, which will be analyzed using Kaplan-Meier methods.

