7. STATISTICAL CONSIDERATIONS

7.1. ADJUSTMENTS FOR COVARIATES AND FACTORS TO BE INCLUDED IN ANALYSES

The following covariates and factors are used in the analyses. For details of their inclusion in the models, see the specific analysis section.

- History of or current presence of esophageal stricture (yes/no)
- Prior positive steroid response to any corticosteroid treatment previously received to treat EoE (yes/no)
- Geographic region (North America/Western Europe see section 7.2)
- History of asthma/allergy
- EREFs score
- PPI status

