8. OUTPUT PRESENTATIONS

Appendix 1 shows conventions for presentation of data in outputs.

Document:

Author: Version Number: 3.0

Version Date: 06NOV2019

Template No.: CS_TP_BS016 Revision 5 Reference: CS_WI_BS005

Effective Date: 01Apr2018

Page 24 of 70

The templates provided with this SAP describe the presentations for this study and the format and content of the summary tables, figures, and listings to be provided by IQVIA Biostatistics.

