16.1.2. MISSING DATA METHODS FOR PRIMARY EFFICACY VARIABLE

For the primary analysis of the primary efficacy variable, any subject who does not meet the definition of responder, will be classified as a non-responder. This includes subjects who withdraw from the study prior to the week 12 histological assessment.

The primary analysis of the primary efficacy variable is via a stratified Cochran-Mantel-Haenzel (CMH) test, as described in section 16.1.3.

A sensitivity analysis, described in section 16.1.4 will be performed with missing response data imputed using multiple imputation, assuming the data are missing at random.

Multiple imputation will be used to provide estimates of the common odds ratio, its 90% confidence interval and associated 1-sided p-value.

The dataset containing subject, dosing group, week 12 histologic response, the two randomization strata, history of asthma/allergy, baseline EREF score, and PPI status will be used as the basis for multiple imputations. Histologic response will be set to missing for those subjects who did not have a Week 12 result for peak eosinophils/HPF (and for whom response status was set to non-responder in the primary efficacy analysis).

The methodology which follows in this section are taken from a 2013 paper by Ratitch, Lipkovich and O'Kelly. The imputation method will be based on logistic regression using the MONOTONE statement of PROC MI in SAS

Author:

Version Number: 3.0

Version Date: 06NOV2019

Template No.: CS_TP_BS016 Revision 5 Reference: CS_WI_BS005

Page 30 of 70

as shown below.

The option NIMPUTE in the PROC MI statement will be used to specify the number of imputed datasets to be generated. The output dataset will contain 500 copies of the original dataset, with the observed values being the same across all datasets, and with imputed values varying from one dataset to another. These multiple copies will be identified by a new variable, Imputation, added to the output dataset by PROC MI.

The SAS Code to perform the imputations is provided below. The SEED and NIMPUTE value are explicitly stated here to enable results to be replicated and quality assured.

```
PROC MI DATA=datain OUT=datain mi SEED=1201913 NIMPUTE=500;
VAR dosegrp strata1 strata2 asthma EREF PPI response;
CLASS dosegrp strata1 strata2 response;
MONOTONE LOGISTIC;
RUN;
```

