Copyright © 2009, 2010, 2012, 2016, 2018 IQVIA. All rights reserved. The contents of this document are confidential and proprietary to IQVIA Holdings Inc. and its subsidiaries. Unauthorized use, disclosure or reproduction is strictly proh bited.

Page 45 of 70

percentages.

No statistical testing will be performed.

16.2.3.4. Analysis of Change from baseline in each of Global EoE Symptom Score, Total EREFs Score, Number of Dysphagia Episodes, 7-day EEsAI total score, 7-day EEsAI VDQ and AMS subscores The change from baseline in each of Global EoE Symptom Score (see section 16.2.1.4), 7-day EEsAI total score (see section 16.2.1.6) and 7-day EEsAI VDQ and AMS subscores (see section 16.2.1.7) will be summarized as continuous variables, and analysis of covariance (ANCOVA) will be used to compare the mean change from baseline in each of the APT-1011 dosing groups to placebo, at the Week 12 visit, with the estimated mean difference, 90% confidence interval of the mean difference and 1-sided p-values provided. This statistical testing at Week 12 is considered descriptive only and no adjustments will be made for multiple comparisons. The ANCOVA models will include the factors described in section 7.1.

All these change from baseline analyses will only include data while subjects are receiving double-blind study drug. Data will not be not included for visits after a histologic non-responder at Week 12 had received single-blind (to subject) APT-1011 3 mg BID in Part 2.

For the analysis of change from baseline in the number of dysphagia episodes (see section 16.2.1.5) and dysphagia free days, for each dose that meets the criterion for statistical significance on the primary efficacy outcome, a Wilcoxon Rank-Sum test will be used to test whether the reduction in the number of dysphagia episodes from baseline is larger for the APT-1011 dosing group compared to the control.

Holm's step-down procedure (Holm, 1979) will be used to control the overall Type I error at 0.05, where the number of doses considered for inferential testing is equal to the number of doses that meet statistical significance for the primary efficacy analysis.

Holm's step down procedure will be implemented as follows:

Let the number of APT-1011 doses that meet statistical significance in the primary efficacy analysis be represented by d (where d is between 1 and 4 inclusive for this study).

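### Minor: the Week 12 ANCOVAs of change in Global EoE, EEsAI total, VDQ and AMS are specified without the outcome's own baseline as a covariate

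*SAP*

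**What the plan says.** SAP 16.2.3.4 compares each APT-1011 dose with placebo at Week 12 by ANCOVA of change from baseline in Global EoE Symptom Score, 7-day EEsAI total, VDQ and AMS. It reports mean differences, 90% confidence intervals and one-sided p-values. The covariates are set by one sentence: "The ANCOVA models will include the factors described in section 7.1".

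SAP 7.1 lists six items: stricture, prior steroid response, region, history of asthma/allergy, EREFs score and PPI status. For the models themselves it refers onward: "For details of their inclusion in the models, see the specific analysis section". The analysis section then refers back to 7.1.

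Protocol 8.8.3 names the method without covariates: "analysis of covariance or Wilcoxon Rank-Sum tests for change from baseline endpoints".

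SAP 16.2.3.4 also sets the status of the results: "This statistical testing at Week 12 is considered descriptive only and no adjustments will be made for multiple comparisons".

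Section 7.1 does not say at which visit the EREFs score is taken. SAP 16.1.2 treats it as a baseline variable in the imputation model: "baseline EREF score, and PPI status will be used as the basis for multiple imputations".

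**The concern.** The baseline of the analysed score is normally the first covariate in an ANCOVA of change, because it is usually the measured variable most closely related to that change. Here the list that serves the histologic-response logistic regression in SAP 16.1.4 is reused for symptom scores. The EREFs ANCOVA in SAP 16.2.1.2 therefore gets its own baseline, if EREFs score means baseline. The four symptom models get an endoscopy score instead.

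Two things are at stake. One is the width of the 90% intervals for the symptom estimates. The other is whether an estimate moves with chance baseline differences, which are ordinary at 20 per arm. There is also a practical point: two competent programmers could deliver different estimates from this text, one adding the baseline by habit and one following the list.

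**Working it through.** **Plan's own figure.** None is stated for these four endpoints. The power figures in protocol 8.1.1 concern the primary endpoint and dysphagia episodes, and this point touches neither.

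**Check of the text.** The covariate list in SAP 7.1, the model sentence in SAP 16.2.3.4 and the method sentence in protocol 8.8.3 were read together. None names a baseline of Global EoE, EEsAI total, VDQ or AMS as a covariate.

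**Inputs.**
- 20 per arm (protocol 8.1).
- Change = visit value minus baseline (SAP 6.7).
- 90% CI (SAP 6.6).
- r, the correlation of baseline with Week 12: not given, assumed 0.3, 0.5 or 0.7.
- k, baseline SD / Week 12 SD: not given, varied below.

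**Precision formula.** With Week 12 variance set to 1:
- variance of change without the outcome's baseline = 1 + k² − 2rk
- residual variance with it = 1 − r²
- variance ratio = (1 − r²) / (1 + k² − 2rk); CI width ratio ≈ its square root

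The first variance minus the second is (k − r)², which is never negative. Apart from the degree of freedom spent, adding baseline cannot lose precision, and it gains nothing when r = k.

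Examples at r = 0.5:
- k = 1: 0.75 / 1.00 = 0.75, square root 0.87.
- k = 1.25: 0.75 / (1 + 1.5625 − 1.25) = 0.75 / 1.3125 = 0.571, square root 0.76.

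**With the planned covariates.** Simulation at 20 v 20 used five binary covariates plus EREFs, correlated 0.3 with the outcome's baseline, in both models. It gives the mean 90% CI width with the outcome's own baseline relative to without it.

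| k | Formula, r = 0.3/0.5/0.7 | Simulated, r = 0.3/0.5/0.7 |
|---|---|---|
| 0.63 | 0.94/0.99/1.00 | 0.97/1.01/1.01 |
| 1 | 0.81/0.87/0.92 | 0.83/0.89/0.94 |
| 1.25 | 0.71/0.76/0.79 | 0.74/0.78/0.82 |

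With r = k (0.5 or 0.7), the simulated ratio is about 1.02. A joint five-arm model gives similar ratios: 0.82/0.88/0.93 at k = 1 and 0.96/1.00/1.00 at k = 0.63.

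**Where k might lie.** Entry rules can compress baseline spread. Protocol 4.2.1 requires "Have a 7-day Global EoE Symptom Score >3 at baseline", and protocol 4.1.4 has subjects "report episodes of dysphagia ≥3 days per 7 days during the last 14 days". If Global EoE were uniform on 4 to 10 at baseline (SD 2.00) and on 0 to 10 at Week 12 (SD 3.16), k would be 2.00 / 3.16 = 0.63. In the other direction, Week 12 scores that cluster low shrink the Week 12 SD and can take k above 1. The documents give no distribution, so the table rows are illustrations.

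**Chance imbalance.** The SE of a baseline difference at 20 v 20 is √(2/20) = 0.32 baseline SD. A difference of one SE moves the change comparison that omits baseline by (r − k) × 0.32 Week 12 SD, before any EREFs adjustment. For r = 0.3/0.5/0.7 the size of the shift is 0.22/0.16/0.09 at k = 1 and 0.10/0.04/0.02 at k = 0.63.

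**The case against.** The strongest reply is that silence is not omission. The sentence says the models include the listed factors; it does not say they include nothing else. Many statisticians take an ANCOVA of change to contain the baseline. The output templates might settle it ("The templates provided with this SAP describe the presentations for this study"), but they were not available. This stands as a possibility: the fault may lie in the wording and not in the programmed analysis. It does not remove the point, because the only model specification available leaves the baseline out.

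It can also be said that 7.1 is read generously for EREFs and literally for the other four outcomes. That is partly fair. The generous reading has support in SAP 16.1.2; nothing comparable supports adding the symptom baselines.

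The magnitude rests on assumed r and k. That stands in full, and it rules out two inferences. A reader might take k = 1 as the most favourable case, but k can exceed 1, and the gain then grows. A reader might also conclude that the entry floor leaves no useful gain for Global EoE. That depends on a uniform Week 12 distribution, which no document supports.

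Finally, protocol 2.5 already reports Week 12 interim results, and SAP 4.2 makes that analysis final for Week 12 endpoints. Pre-specification cannot be restored. The added models bring 4 outcomes × 4 doses × 2 analysis sets = 32 further descriptive contrasts. Labelling limits this cost but does not remove it.

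**Conclusion.** The point holds as a minor, nearly free improvement. As written, the four symptom ANCOVAs adjust for EREFs score and five other factors but not for the outcome's own baseline.

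A reader might infer that the symptom comparisons are biased or invalid, or that dose conclusions depend on them. The documents do not support that. Randomisation keeps the change comparison unbiased on average, the tests are labelled descriptive, and neither the primary gatekeeping sequence nor the Holm procedure for dysphagia uses these models. Nor do the documents show that the baseline was deliberately excluded.

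The size of the gain is uncertain. At 20 v 20 with r between 0.3 and 0.7, the 90% intervals would be about 6% to 17% narrower at k = 1. At k = 0.63 the effect runs from 3% narrower to 1% wider, and at k = 1.25 from about 18% to 26% narrower. The least favourable case (r = k) is about 2% wider. No conclusion for a particular endpoint is justified. The EREFs ANCOVA is unaffected if EREFs score means baseline.

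**What to change.** In SAP 16.2.3.4, state that the ANCOVA models for change in Global EoE Symptom Score, EEsAI total, VDQ and AMS include the section 7.1 factors and the baseline value of the endpoint being analysed. Record the change in SAP 3.3.

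Label these models as specified after the interim analysis, and show them beside the original models, for FAS and for the ITT repeat under SAP 16.4.1, all as descriptive. If the templates or programs already include the baseline, say so in the text instead.

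Leave the EREFs ANCOVA and the dysphagia Wilcoxon/Holm test as they are.

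The cost is one sentence, one entry in SAP 3.3, one degree of freedom per model, and a rerun of four analyses on two populations. No new data are needed: protocol Table 4-1 already collects Global EoE and the 7-day EEsAI, from which VDQ and AMS are derived, at Visit 3.

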## 6.2.8.2 Secondary Efficacy Endpoints

The following secondary efficacy endpoints will be evaluated:

- EoE sustained response: percentage of subjects who met the primary endpoint (histology) at Week 12 and maintained the primary endpoint at Week 26 and Week 52;
- Change from baseline EREFs at Week 12, Week 26, and Week 52;
  - Endoscopic changes will as per the EREFs evaluation based on the following endoscopic features: edema, rings, exudates, furrows, stricture, and several miscellaneous features (crepe paper esophagus, narrow caliber esophagus, and esophageal erosions);
- Percentage of subjects with a peak eosinophils/HPF number <1 and <15 at Week 12, Week 26, and Week 52;

- Change from baseline Global EoE Symptom Score assessed prior to randomization, which will be assessed for the 7-day period prior to the following study visits: Week 4, Week 8, Week 12, Week 14, Week 18, Week 22, Week 26, Week 28, Week 36, Week 44, and Week 52;

- Dysphagia: Change in the number of dysphagia episodes at baseline (14-day period prior to randomization) compared with the 14-day period prior to the time point of interest (Week 12, Week 26 and Week 52).
- Change from baseline 7-day EEsAI total score assessed prior to randomization to those assessed at Week 12, Week 26, and Week 52;
- Change from baseline 7-day EEsAI subscores to those assessed at Week 12, Week 26, and Week 52;
- Percentage of subjects with mean 7-day EEsAI total score <20 to those assessed at Week 12, Week 26, and Week 52;
- Change from baseline PGIS assessed prior to randomization at Weeks 4, 8, 12, 14, 18, 22, 26, 28, 36, 44, and 52;
- PGIC at Weeks 4, 8, 12, 14, 18, 22, 26, 28, 36, 44, and 52.
- Assessment of treatment failure and relapse, including:
  - o Percentage of histologic non-responders by dose at Week 12, Week 26, and Week 52;
  - Percentage of subjects requiring emergency endoscopic food dis-impaction by dose before Week 14, between Week 14 and Week 28, and between Week 28 and Week 52;
  - Percentage of subjects requiring esophageal dilation by dosing group and part of the study.

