6.6. STATISTICAL TESTS

The default significant level will be 5%; confidence intervals will be 90% and all tests will be one-sided.

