7.4. MULTIPLE COMPARISONS/ MULTIPLICITY

The primary analysis of the primary efficacy variable will be performed using a gatekeeping strategy to preserve Type I error. This strategy is described in section 16.1.3.

The analysis of the secondary efficacy parameter of number of dysphagia episodes will use a Holm-Step down procedure (Holm, 1979). This is described in section 16.2.3.4.

All other statistical testing performed is considered descriptive only and no adjustments will be performed for multiplicity.

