- The change from baseline in the EREFs total score will be summarized as continuous variables, and analysis of covariance (ANCOVA) will be used to compare the mean change from baseline in each of the APT-1011 dosing groups to placebo, at the Week 12 visit, with the estimated mean difference, 90% confidence interval of the mean difference and 1-sided p-values provided. This statistical testing at Week 12 is considered descriptive only and no adjustments will be made for multiple comparisons.
- The ANCOVA models will include the factors described in section 7.1.

•

16.2.1.3. Peak eosinophils/HPF number <1 and <15 at Week 12, Week 26, and Week 52 Subjects who had withdrawn prior to each visit will not have results imputed, and percentages will be based on the number of subjects with EGD results assessed at the visit.

Subjects with a result of <1/HPF will also be counted as having a result of <15/HPF.

- 16.2.1.4. Change from baseline Global EoE Symptom Score at each post-baseline visit The global EoE symptom score, ranging from 0 to 10 will be provided directly to IQVIA Biostatistics with no derivation required. This will be retrieved from the diary.
- 16.2.1.5. Change from baseline in the number of dysphagia episodes at Week 12, Week 26 and Week 52

The number of dysphagia episodes for a subject will be determined from the 14 day evening diary completed prior

Author:

Version Number: 3.0

Version Date: 06NOV2019

Template No.: CS_TP_BS016 Revision 5 Reference: CS_WI_BS005

Page 39 of 70

to each of Week 12, Week 26 and Week 52. The number of episodes for each day will have 2 components a real time episode component along with the CRF entry of the number of dysphadia free days in the last 24 hours. First a day must be identified as a valid day. A day is considered valid if the subject awnsers yes to the CRF question "In the last 24 hours, did you have any difficulty with food or pills going down."

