16.2.3. Analysis of Secondary Efficacy Variables

Statistical tests to compare each APT-1011 dosing group with placebo will be performed for some secondary efficacy endpoints as described in the following sections, but the corresponding p-values will be considered as descriptive rather than inferential. The analyses and summaries of secondary efficacy variables will be performed for FAS analysis set.

16.2.3.1. Analysis of EoE sustained response: maintenance of ≤6 peak eosinophils/HPF at Weeks 26 and 52 for histologic responders at Week 12

The frequency and percentage of histologic responders at Week 12 who maintained response at each of Week 26 and Week 52 will be provided for each randomized dosing group. Only histologic responders at Week 12 will be included in the summary.

No statistical testing will be performed.

16.2.3.2. Analysis of change from baseline PGIS and change from baseline in each of the EEsAI items trouble swallowing, duration of trouble swallowing and pain when swallowing

For each of the two PGIS questions (see section 16.2.1.9) and for the EEsAI items trouble swallowing frequency, duration of trouble swallowing and pain when swallowing, shift tables will be provided for the results at baseline and at each post-baseline visit, for each randomized dosing group. Data will not be not included for visits after a histologic non-responder at Week 12 had received single-blind (to subject) APT-1011 3 mg BID in Part 2.

No statistical testing will be performed.

16.2.3.3. Analysis of percentage of subjects with a peak eosinophils/HPF number <1 and <15 and percentage of subjects with 7-day EEsAI total score <20

The number and percentage of subjects in each of these categories will be presented by visit for each of the randomized dosing groups.

The summaries will only include data while subjects are receiving double-blind study drug. Data will not be included for visits after a histologic non-responder at Week 12 had received single-blind (to subject) APT-1011 3 mg BID in Part 2.

Patients who do not have assessments at the respective visits will not be included in the denominator for

Author:

Version Number: 3.0

Version Date: 06NOV2019

Template No.: CS TP BS016 Revision 5

Reference: CS WI BS005

Effective Date: 01Apr2018

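### The one error-controlled secondary test (dysphagia) fixes neither its measure nor its visit, so overall control at 0.05 is not assured as written

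*SAP*

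**What the plan says.** Dysphagia is the only secondary outcome with multiplicity control. SAP 7.4 states: "The analysis of the secondary efficacy parameter of number of dysphagia episodes will use a Holm-Step down procedure", and makes all other testing outside the primary analysis descriptive.

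SAP 16.2.3.4 sets out the test. Its lead-in is "For the analysis of change from baseline in the number of dysphagia episodes (see section 16.2.1.5) and dysphagia free days, for each dose"; only doses already significant on the primary outcome qualify. A Wilcoxon rank-sum test then asks whether the reduction in episodes is larger than on placebo. On error control the section says: "Holm's step-down procedure (Holm, 1979) will be used to control the overall Type I error at 0.05". The family is sized by doses alone, as the same sentence goes on to explain: "where the number of doses considered for inferential testing is equal to the number of doses that meet statistical significance". Significance there refers to the primary analysis. The hypothesis written with the Holm steps concerns episodes only. Neither names a visit.

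The cross-reference, SAP 16.2.1.5, is headed "Change from baseline in the number of dysphagia episodes at Week 12, Week 26 and Week 52". Protocol 6.2.8.2 defines the same three occasions: "compared with the 14-day period prior to the time point of interest (Week 12, Week 26 and Week 52". Protocol 8.8.3 repeats the Wilcoxon and Holm text, also without a visit. By contrast, the ANCOVA paragraph earlier in SAP 16.2.3.4 is tied to Week 12.

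The introduction to SAP 16.2.3 says of tests on some secondary endpoints: "but the corresponding p-values will be considered as descriptive rather than inferential". It makes no exception for dysphagia. Tests are one-sided at 5% (SAP 6.6).

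**The concern.** A controlled claim needs one defined hypothesis per dose. Here three things are left open.

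- **Measure.** The lead-in puts dysphagia-free days beside episodes. Free days are derived in SAP 16.2.1.5 but are not among the secondary endpoints in Protocol 6.2.8.2. Benefit on free days is an increase, whereas the test is written for a reduction.
- **Visit.** The text points to a variable with three visits and chooses none.
- **Correction.** Holm's divisor counts doses. Nothing accounts for a second measure or further visits, so each could be given its own full 0.05.

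At stake is whether a statement that a dose reduces dysphagia at a controlled 5% level can be traced to one result fixed in advance. For Weeks 26 and 52 there is a further question: whether the comparison is still between randomized groups.

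**Working it through.** **Inputs.** Overall level 0.05, Holm over d = 1 to 4 doses (SAP 16.2.3.4); one-sided tests (SAP 6.6); 20 per arm, SDs 4.5 and 7.5, response rates 60% for three doses, 20% for 1.5 mg HS and 10% for placebo, 20% dropout before Week 26 and again before Week 52 (Protocol 8.1.1). Correlations are assumed; the documents give none.

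**Step 1: the plan's own power figures.** Average SD = √((4.5² + 7.5²)/2) = √38.25 = 6.18. Standard error = 6.18 × √(2/20) = 1.96.

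- 5.0 episodes, one-sided 0.05: Φ(5.0/1.96 − 1.645) ≈ 82%; 80.7% with the t distribution.
- 6.3 episodes, 0.05/4 = 0.0125: Φ(6.3/1.96 − 2.241) ≈ 84%; 80.9% with t.

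Both agree with the stated 80%. The calculation allows for up to four doses, one measure and full arms.

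**Step 2: Type I error if each measure or visit has its own Holm procedure.** With no true dysphagia effect, Holm rejects something only if the smallest p-value is at most 0.05/d. For d = 1 and two independent measures, the error is 1 − 0.95² = 0.0975. With a shared placebo arm and correlation r between measures, simulation of 400,000 trials gives:

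| Confirmatory set | d = 1 | d = 2 | d = 3 | d = 4 |
|---|---|---|---|---|
| One measure, one visit | 0.050 | 0.046 | 0.043 | 0.041 |
| Two measures, Week 12, r = 0.5 | 0.088 | 0.081 | 0.077 | 0.074 |
| Two measures, Week 12, r = 0.9 | 0.068 | 0.063 | 0.061 | 0.059 |

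The one-measure figures varied by about 0.001 between runs.

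**Step 3: who is left at Weeks 26 and 52.** SAP 16.2.3.4 uses only data on double-blind drug and drops Week 12 non-responders once they switch. I read this as covering the dysphagia test, which the section heading includes. Expected numbers before dropout are 20 × 0.10 = 2 on placebo, 20 × 0.60 = 12 on each of three doses, and 20 × 0.20 = 4 on 1.5 mg HS.

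The smallest possible one-sided exact Wilcoxon p-values are:

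- 12 against 2: 1/C(14,2) = 1/91 = 0.011, just under 0.05/4 = 0.0125, so with d = 4 the first Holm step needs complete separation;
- 10 against 2, after 20% dropout on active drug: 1/C(12,2) = 1/66 = 0.015, which cannot pass that step;
- 4 against 2: 1/C(6,2) = 1/15 = 0.067.

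**Step 4: both features together.** Applying the response rates, dropout and Wilcoxon tests with d = 4 and correlations from 0 to 0.7 (3,000 trials per setting, Monte Carlo standard error about 0.004):

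| Confirmatory set | Error |
|---|---|
| Episodes, Week 12 | 0.036–0.043 |
| Both measures, Week 12 | 0.062–0.081 |
| Episodes, three visits | 0.043–0.052 |
| Both measures, three visits | 0.077–0.101 |

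The second measure produces most of the inflation; the later visits add little because almost no placebo subjects remain. This simulation makes histologic response independent of dysphagia, so it shows inflation only. It cannot show the bias from comparing groups selected on a post-randomization response.

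**The case against.** The strongest reply is that the documents already favour a single test. SAP 7.4 gives Holm to the number of episodes and makes other testing descriptive. The sentence that mentions free days goes on to define the test as a reduction in episodes, and the written hypothesis concerns episodes only. Protocol 8.8.2 calls Part 2 mainly descriptive, SAP 4.2 makes the Week 12 lock final for Week 12 endpoints, and the power case rests on 20 against 20, which exists only at Week 12. On that reading Holm keeps the error at or below 0.05.

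Most of this stands, and it rules out several stronger readings:

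- *That 0.05 is breached outright.* This follows only if free days or several visits are tested confirmatorily, which the documents do not say.
- *That six results are available at 0.17 to 0.27.* Such figures treat Weeks 26 and 52 as full-size comparisons, which the SAP's own exclusion prevents.
- *That the SAP makes every secondary p-value descriptive.* SAP 16.2.3 refers to some endpoints, and SAP 7.4 and 16.2.3.4 are more specific.
- *That free days lie outside the protocol.* They are not in its secondary list, but the exploratory list is not readable in this copy. The output templates, which might name a visit, are also not available.

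What the reply does not remove is the text. Episodes at Week 12 can be inferred but is nowhere stated, and the lead-in still names a second measure.

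**Conclusion.** The concern holds in this form: overall control at 0.05 is not assured, because the confirmatory measure and visit are not fixed and Holm corrects over doses only.

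With episodes at Week 12 alone, the error is 0.041 to 0.050. With both measures at Week 12, each under its own Holm procedure, it is about 0.06 to 0.09 for assumed correlations of 0.9 to 0.5. Correlations near zero are implausible, since both measures come from the same 14-day diary. At Weeks 26 and 52 the objection is mainly validity: a responder subset with about 2 placebo subjects should not carry a formal claim.

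Protocol 2.5 reports that the primary endpoint was met at every dose in the interim data. If that means all four gated tests succeeded, d = 4 and the two-measure range is 0.059 to 0.074. SAP version 3.0 (06 November 2019) is later than the date printed on the protocol pages (16 July 2019). A reader might infer that the choice was left open with results in hand; the documents do not say when free days were added and do not support that inference.

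The primary analysis is unaffected.

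**What to change.** In SAP 7.4 and 16.2.3.4, and in Protocol 8.8.3, write in substance: *The only Holm-controlled secondary hypothesis is the change from baseline in the number of dysphagia episodes at Week 12, for each dose significant on the primary outcome. Dysphagia-free days, and all dysphagia results at Weeks 26 and 52, are descriptive.* In SAP 16.2.3, exempt this test from the general statement about descriptive p-values. Date the clarification and record its timing relative to the Week 12 unblinding.

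If a formal claim on free days is wanted, test them at Week 12 for a dose only after that dose's episode hypothesis is rejected, with benefit defined as an increase. The level must be stated too. Giving each dose 0.05/d for both steps, with nothing passed between doses, keeps the total at d × 0.05/d = 0.05. Keeping Holm for episodes and adding free-day tests at 0.05/d would not: with d = 2, one true episode effect releases 0.05 to the other dose, and a free-day test at 0.025 allows up to 0.075.

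**Cost.** Wording changes in the SAP and protocol, and no formal claims on free days or on Weeks 26 and 52. The episode test loses no power. By comparison, splitting the level equally over two measures and four doses (0.05/8 = 0.00625) would cut power at 6.3 episodes from 81% to 72%.
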